### 5.6.7 Unknown Risks

The overall risk classification of this research is unknown.

## 5.7 Data Analysis and Statistical Considerations

Within the Phase 1 portion of this study, the MTD for BMX-001 administered in conjunction with temozolomide and radiation treatment will be determined for patients newly diagnosed with high grade glioma. A CRM model as described in section 16.4.1.2 will be used to determine the dose with the estimated DLT rate closest to the target DLT rate of 0.25. This Phase 1 study will be conducted in two stages. The first stage involves dose escalation in successive cohorts of 3 patients until a DLT is observed. The second stage commences with the observation of a DLT. Within the second stage, all accumulated data will be used within the context of a one-parameter model to determine the appropriate dose for each subsequent cohort of 3 patients. When the toxicity outcomes associated with patients within a cohort within the second stage are known, the one-parameter logistic model will be re-estimated by the study's statistical team using all available data. Based upon this re-estimated model, the dose level that results in a DLT rate nearest to the target DLT rate will be determined, and used to treat the next patients, subject to a dose escalation restriction. That restriction requires that the dose for the next patient cannot be more than one level higher than that of the current patient.

In Phase 2, the study's primary endpoint is overall survival, defined as the time between randomization and death. A logrank test will be used to compare the survival experience of the two treatment arms. An intent-to-treat philosophy will be used in the analysis of survival by including all patients who are randomized in the analysis. Among the secondary endpoints are two that are of particular interest: cognitive function and thrombocytopenia. The mean change in cognitive functioning between baseline (enrollment) and week 24 within each treatment arm will be computed, and analysis of covariance will be conducted to compare groups with respect to that change. Treatment group assignment will be included in the model as a predictor, and the baseline measure of cognitive function will be included as a covariate. The proportion of patients who experience grade 3 or 4 thrombocytopenia during concurrent temozolomide and radiation, a period that terminates 2 weeks after completion of radiation treatment, will be summarized. A chi-square test will be conducted to compare the prevalence of such thrombocytopenia observed in patients with and without BMX-001 [1].

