#### Hematologic Criteria

- 1. Grade 4 neutropenia (ANC, including bands,  $\leq$  500 cells /µl);
- 2. Grade 3 thrombocytopenia (platelet count of  $\leq$  50,000 cells/µl);

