#### 16.5.2.2 Secondary Objective #2 for Phase 2: Thrombocytopenia

The proportion of patients who experience grade 3 or 4 thrombocytopenia during concurrent temozolomide and radiation will be estimated within each treatment group. The proportion of patients who experience a platelet count less than 100K during concurrent temozolomide and radiation will also be estimated within each treatment group. The period of observation for these events will extend until 2 weeks after completion of radiation treatment. For both endpoints, a chi-square test will be conducted to compare the prevalence of such thrombocytopenia observed in patients with and without BMX-001.

In addition, the longitudinal patterns of platelet count over time will be explored in mixed linear models that account for within patient correlation. These longitudinal patterns will focus on the time period during BMX-001 treatment administration that continues for 2 weeks after radiation treatment is completed.

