10.1 ENDPOINT

The proportion of patients who experience grade 3 or 4 thrombocytopenia during concurrent temozolomide and radiation will be estimated within each treatment group. The proportion of patients who experience a platelet count less than 100K during concurrent temozolomide and radiation will also be estimated within each treatment group. The period of observation for these events will extend until 2 weeks after completion of radiation treatment.

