10.2 METHOD OF ANALYSIS

For both endpoints described in Section 10.1, a chi-square or Fisher's exact test will be conducted to compare the prevalence of such thrombocytopenia observed in patients with and without BMX-001.

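### Both thrombocytopenia comparisons ignore the screening platelet count; the unadjusted test is valid but may forgo some power, by an amount that depends on a correlation the documents do not give

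*Protocol*

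**What the plan says.** Protocol 5.7 singles out cognition and thrombocytopenia among the secondary endpoints. Cognition is compared by analysis of covariance with its baseline value. For grade 3-4 thrombocytopenia, "A chi-square test will be conducted to compare the prevalence of such thrombocytopenia observed in patients with and without BMX-001".

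Protocol 16.5.2.2 adds a second endpoint, a platelet count below 100K, and states: "For both endpoints, a chi-square test will be conducted to compare the prevalence of such thrombocytopenia observed in patients with and without BMX-001". SAP 10.1 keeps both endpoints, and SAP 10.2 reads: "For both endpoints described in Section 10.1, a chi-square or Fisher's exact test will be conducted". No covariate or stratification factor is named in any of the three places.

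The baseline value exists. Inclusion criterion 7 requires at least 125,000 platelets/µl, protocol 13.1 includes a complete blood count at screening, and the footnotes to Table 4 say that this count includes platelets. Randomisation (protocol 9.1.9) is stratified by grade and institution only.

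Protocol 16.5.2.2 also plans exploratory mixed linear models of platelet counts over time. It does not name baseline as a covariate there, and SAP section 10 does not carry these models forward. SAP section 3 gives the SAP precedence where methods differ substantially.

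**The concern.** Each endpoint records whether a later count falls below a fixed value: 100K, or grade 3, which protocol 13.4.1 reads as 50,000 or less. How far a patient must fall depends on where that patient starts. The starting count is therefore a natural prognostic covariate, known before treatment in both arms.

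Two things are at stake in a comparison that the plan highlights:

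- **Power.** If the starting count predicts the nadir, adjusting for it increases power at no cost in patients.
- **Chance imbalance.** Randomisation balances platelets only by chance. An unadjusted test cannot separate a difference in starting counts from a drug effect in the trial at hand.

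**Working it through.** **1. Inputs from the documents.** Control rate of grade 3-4: 15%. Detectable rate: 4% with 80 per arm (protocol 16.5.5.3), or 3.7% with 78 in Arm A and 71 in Arm B (SAP 10.3.2). Both power statements are one-tailed at 0.05. Rate below 100K without BMX-001: 9/20 = 45%, from the off-protocol cohort in protocol 7.4.

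**2. Inputs that are assumptions.** The correlation r between log baseline and log nadir platelets is shown at 0.3, 0.5 and 0.7. The Arm A rate below 100K is set at 27%.

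**3. The plan's own power.** Arcsine formula: power = Φ(h·√[n₁n₂/(n₁+n₂)] − 1.645), where h = 2·asin√p₁ − 2·asin√p₂.

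- 80 per arm, 15% v 4%: h = 0.393; 0.393 × √40 − 1.645 = 0.84; power 79.9%. Exact enumeration of the uncorrected chi-square gives 80.1%.
- 71 v 78, 15% v 3.7%: h = 0.408; 0.408 × √37.17 − 1.645 = 0.84; power 80.1%. Exact: 79.3%.

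Both stated figures of 80% reproduce.

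**4. Distance to the cut-off.** From the entry floor of 125,000, crossing 100K takes a fall of 1 − 100/125 = 20%, and reaching 50K takes 1 − 50/125 = 60%. From 250,000, a purely illustrative start, the falls are 60% and 80%.

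**5. Power with baseline adjustment.** The simulation uses 78 v 71 patients and one-sided 0.05. An event is a latent normal nadir below the cut-off, correlated r with standardised log baseline. The unadjusted chi-square is set against the score test for arm in a logistic model with baseline. Ranges are across repeated runs of at least 3,000 trials per cell; the simulation error of one power figure is about √(0.75 × 0.25/3,000) = 0.8 points.

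| Endpoint | r | Unadjusted | Adjusted | Gain (points) |
|---|---|---|---|---|
| Grade 3-4, 15% v 3.7% | 0.3 | 78-80% | 80% | about 1 |
| | 0.5 | 78-80% | 83-84% | 3-5 |
| | 0.7 | 78-80% | 87-89% | 8-9 |
| Below 100K, 45% v 27% | 0.3 | 73-74% | 75-78% | about 3-4 (2-4 across runs) |
| | 0.5 | 73-74% | 80-82% | 7-8 |
| | 0.7 | 73-74% | 88% | 14-15 |

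Simulated type I error of the adjusted test was 4.1-6.2% across runs, that is, about 5%.

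A separate model with 80 per arm and log-normal entry counts truncated at 125,000 gave the same pattern. For grade 3-4 (15% v 4%), adjusted power was 83% at r=0.5 and 86-87% at r=0.7, against about 80% unadjusted.

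**6. Few events.** Expected grade 3-4 events are 0.15 × 71 + 0.037 × 78 = 10.65 + 2.89 = 13.5. With the Firth penalised likelihood-ratio test, power was about 81%, 82% and 87% at r = 0.3, 0.5 and 0.7.

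**7. Chance imbalance.** The standard error of the difference in mean standardised baseline is √(1/78 + 1/71) = 0.164. So P(difference > 0.2 SD favouring Arm A) = P(Z > 1.22) = 11%, about 1 trial in 9. At a difference of 0.2 SD, with r=0.5 and a common rate of 45%:

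- Shift of the statistic: 0.396 × (0.5 × 0.2)/0.0816 = 0.485, where 0.396 is the normal density at the 45% point and 0.0816 = √(0.45 × 0.55) × 0.164.
- Conditional SD: √(1 − 0.25 × 0.396²/0.2475) = 0.917.
- Conditional one-sided error: P(Z > (1.645 − 0.485)/0.917) = P(Z > 1.265) = 10%.

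Larger differences in the same direction raise it further; differences the other way lower it below 5%.

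**The case against.** The strongest reply is that nothing here is wrong. Under 1:1 randomisation an unadjusted chi-square is valid, the power statement is written for that test, and it reproduces. That stands.

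A reader might infer that patients start at very different distances from the cut-offs and that the plan therefore wastes power. The documents do not show this. They give the 125,000 floor but neither the spread of entry counts nor r. The screening count can be up to three weeks old, and Table 4 lists no blood count on Day -5 to 0 or in Week 1, so a high r cannot be presumed. At r=0.3 the only thrombocytopenia endpoint with a power statement gains about 1 point.

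A reader might also infer that chance imbalance inflates the false-positive rate. It does so only conditionally. Averaged over randomisations the error is about 5%, so alpha already covers it. An imbalance above 0.2 SD in either direction occurs in about 22% of trials, but only half of these favour Arm A.

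The larger gains are for the 100K endpoint, whose 27% is assumed and whose 45% comes from 20 patients that the protocol itself says cannot be directly compared.

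The contrast with cognition is weak, because that outcome is a continuous change score. The other binary efficacy endpoint, radiographic response, is also compared unadjusted.

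The protocol's mixed models use the platelet data, but they test neither proportion and are absent from SAP section 10, so they do not close the gap. Dichotomising the counts and the Fisher option may cost more power than omitting the covariate; those are separate points.

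**Conclusion.** The point holds as a missed, inexpensive improvement. It is not an error: the planned test is valid and the stated 80% power is correct.

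The power forgone for grade 3-4 is about 1 point if r is 0.3 and 8-9 points if r is 0.7. For platelets below 100K it is about 3-4 to 14-15 points over the same range. These figures rest on a latent-normal model, on values of r that the documents do not supply and, for the 100K endpoint, on the assumed 27%. No simulated scenario showed a meaningful loss of power from adjusting.

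The stronger conclusions, that power is certainly wasted or that the overall error rate is inflated, are not supported. What can be said about error is conditional: if Arm A happens to start 0.2 SD higher, the unadjusted 100K test has a one-sided error of about 10% at r=0.5, and an imbalance at least that large in that direction arises in about 1 trial in 9.

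**What to change.** In SAP 10.2 and protocol 16.5.2.2:

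- Make the between-arm test for both endpoints a logistic regression on arm and log screening platelet count, with no other covariate.
- Use Firth penalisation for grade 3-4, because only about 14 events are expected.
- Report a standardised risk difference with its confidence interval. The power figures above are for the tests; the performance of this estimate was not simulated.
- Keep the chi-square or Fisher result as supportive. The existing power statements can stay as they are.

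The cost is a change of wording and one extra model on data already collected. The downside is little gain on grade 3-4 if r turns out to be low.

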# 6 STUDY SCHEMA

Figure 1: Study Schema for Phase 2 Portion of the Study. Review the table in Section 13 for a complete list of study procedures.

# 7 BACKGROUND AND SIGNIFICANCE

## 7.1 Study Disease

Primary brain tumors represent 1% of all diagnosed cancers, but are among the most lethal [3]. Median survival for adults with HGG (WHO grade III and IV) is poor and ranges from 9-15 months after diagnosis. Most high grade CNS tumors are highly resistant to current available therapies. The standard of care for newly diagnosed high-grade gliomas (HGGs) involves surgical resection, followed by standard RT with concurrent TMZ, and subsequent adjuvant TMZ. Patients with HGG not only contend with oncologic diagnosis but also a neurologic one that can lead to cognitive dysfunction.

# 7.2 Radiation-Induced Damage during Brain Tumor Treatment

During the disease treatment course, the nervous system can be damaged by all parts of the multimodal approach. In particular, RT can lead to the generation of reactive oxygen species which in turn leads to oxidative stress [4]. The oxidative stress is not only responsible for the damaging of the DNA and killing of the tumor cells but also leads to damage of the white matter [5]. Central nervous system toxicity from RT is defined as acute, early delayed, and late delayed [6]. Acute form can occur during RT and is more apparent with doses > 60 Gy. This is rarely seen with the modern approach to standard chemoradiation in adult glioma patients. Early delayed encephalopathy and late delayed encephalopathy are still seen with some frequency in the HGG population. Early delayed encephalopathy is characterized clinically by somnolence, attention deficits, and gait impairment. This occurs between one to six months after RT and is thought to be due to transient demyelination. Late delayed encephalopathy occurs months to years after RT and, clinically, patients demonstrate a pattern of subcortical dementia (short-term memory loss, problems with gait and attention). Mechanism of action involves damage to the supporting vasculature, which in turn leads to demyelination and, in severe cases, RT necrosis. The impact to patients is cognitive impairment and subsequent degradation of HRQoL. In fact, 50-90% of brain tumor patients that received RT demonstrated cognitive impairment, if they survived >6 months from RT [7-10]. In summary, the oxidative stress produced by RT in brain tumor patients leads to white matter damage, subsequent cognitive impairment, and finally quality of life impairment.

# 7.3 Cognition and HRQoL in HGG

Cognitive dysfunction, whether it develops due to the underlying tumor, treatment, or use of medications such as anti-epileptics and corticosteroids, usually comes in concert with a reduction in HRQoL. In both newly diagnosed and recurrent HGGs, reduction in cognitive function was associated with a reduction in reported HRQoL [11-13]. When compared to healthy controls or patients with other malignancies, high-grade glioma patients experience a great degree of cognitive impairment and related reduction in HRQoL [13].

Before and during treatment for HGG, adult patients experience a decline in perceived HRQoL[14,15]. Liu defines HRQoL as "a concept that encompasses the multidimensional well-being of a person and reflects an individual's overall satisfaction with life" [15]. For brain tumor patients, focal neurological dysfunction, whether cognitive or physical, fatigue associated with treatment, symptoms such as nausea and anorexia associated with treatment, and other common symptoms such as insomnia, seizures, and headaches all have negative impacts on HRQoL. Overall, functionality and HRQoL are particularly important in brain tumor patients since these patients have more dysfunction in these areas than age-matched controls with non-small lung cancer [13]. In a large prospective study by Budrukkar and colleagues of HRQoL in brain tumor patients, they found that HRQoL, as rated by scores from questionnaires, was low before starting any type of treatment, and factors associated with poorer HRQoL included patients with poor performance status, illiteracy, and a more aggressive nature of the tumors [16]. Moreover, HRQoL is dependent upon the physical function and cognition of the brain tumor patients with better physical function and better cognitive

function reported having a higher level of HRQoL [11]. Liu and colleagues discuss how these symptoms and signs are interrelated and should not be studied alone because cognitive decline/ dysfunction were associated with increased fatigue and poorer performance status [15,17,18]. During concurrent chemoradiation, brain tumor patients experience a decline in relative HRQoL particularly due to fatigue and changes in cognition [7,19].

In order to capture fully the many aspects of cognition and HRQoL, we have utilized both objective and subjective measures to evaluate issues with cognition, fatigue, HRQoL, and mood. Cognition can be measured objectively with standardized cognitive testing. One testing model is CNS Vital Signs®, a computerized battery. CNS Vital Signs® has been validated and is being used extensively in our research, not only primary brain tumor patients, but also patients with other forms of cancer [20]. Modalities within CNS Vital Signs® assess cognitive flexibility, complex attention, executive functioning, psychomotor speed, processing speed, verbal and visual memory. We published the cognitive performance of newly diagnosed HGG using this battery and showed that they had measurable cognitive dysfunction in all domains [21,22]. After diagnosis, newly diagnosed HGG patients exhibit deficits in all tested cognitive domains with standardized scores ranging from 90.1 to 72.7 (a score of 100 represents mean standardized score for normative age-matched subjects). These deficits continue throughout the treatment and disease trajectory with lower performances present after radiotherapy and 24 weeks after initial diagnosis. Importantly, performance on neurocognitive testing is independent of education, grade, gender, and tumor location, but Karnofsky Performance Scale (KPS) and surgery extent are important predictors of neurocognitive performance. Moreover, long-term survivors of primary HGG (WHO grade IV) continued to exhibit cognitive dysfunction despite having achieved an improved survival [23]. Therefore, there is an unmet need to improve the cognitive outcomes in patients with newly diagnosed HGG, irrespective of survival outcomes. Another testing model called The Brief Assessment of Cognition (BAC) is a battery of tests is implemented through an iPad-based app (VeraSci). The BAC was created by Richard Keefe, Jim Gold, Terry Goldberg, and Philip Harvey as a pen-and-paper measure for the repeated assessment of cognition in clinical trials for schizophrenia (referred to as BACS) [24]. With published normative data [25] and over a decade of use, the BACS is the subject of approximately 100 peer-reviewed papers and has been used in over 30 multisite clinical trials across a range of patient groups. To reduce rater burden and promote standardization of neurocognitive testing in clinical trials, the BAC is now implemented as an iPad-based app [26]. The BAC App assists raters in administration and scoring of all subtests included in the original pen-and-paper instrument.

Subjectively, HRQoL is measured using patient-reported outcome questionnaires known as PROs. A commonly used instrument is the Functional Assessment of Cancer Therapy-Brain (FACT-Br) which has been used extensively and has been documented to identify key QoL problems for brain tumor patients [27]. Other standardized questionnaires will include Functional Assessment of Cancer Therapy-Fatigue, Functional Assessment of Cancer Therapy-Cognition, and Beck Depression Inventory.

RT in patients with HGG causes oxidative stress in brain tissue, which can lead to white matter damage, subsequent cognitive impairment, and HRQoL impairment. White matter damage due to RT can be detected using serial MRI diffusion tensor/susceptibility imaging [28-30]. This damage is evident and detectable using serial MRI diffusion tensor/susceptibility imaging both immediately and subsequently after the completion of RT in HGG patients [31-33]. Therefore, MRI diffusion tensor/ susceptibility imaging can serve as a biomarker of white matter damage caused by RT in HGG patients. In fact, early changes in the parahippocampal white matter seen on MRI diffusion tensor/ susceptibility imaging have been linked to late decline in verbal memory in patient that received RT [34].

Interventions to improve cognition and HRQoL in brain tumor patients have included stimulants such as methylphenidate and modafinil. Clinical trials with methylphenidate in brain tumor patients

undergoing RT were discontinued in early stages because interim analysis did not show any evidence of effectiveness [35]. Studies with modafinil did show some positive effects on HRQoL in brain tumor patients, but the study was not placebo-controlled [36]. Medications to treat Alzheimer's disease are being explored in the glioma population. Donepezil, a reversible acetylcholinesterase inhibitor used in mild to moderate Alzheimer's dementia, has been studied in primary brain tumor patients. In this Phase 2 study, donepezil improved cognition, mood, and HRQoL in irradiated brain tumor patients [37]. More rigorous Phase 2 studies are needed to evaluate the effectiveness of anti-Alzheimer's agents in glioma patients and side effects from these medications have limited their usefulness. Therefore, new approaches and more clinical studies are needed to evaluate interventions in regards to cognition and HRQoL in primary brain tumor patients.

In Phase 1, all fifteen subjects have completed quality of life evaluations and cognitive evaluations for the time points before concurrent chemoradiation and after concurrent chemoradiation. Cognitive testing included Hopkins Verbal Learning Test-Revised (HVLT-R), Trails Making A and B Tests, and Controlled Oral Wood Association Test (COWA). While it is early to assume cognitive protection of BMX-001, we have early findings that there is improvement of verbal memory as demonstrated by improved scores on HVLT-R, and no degradation in performance on Trails Making B Test (Figure 2) and COWA. This is notable because these arethe primary cognitive tests that reveal poorer performance in HGG patients after RT.

While promising, these results, along with the quality of life data, will need to be considered more fully after more subjects are treated with BMX-001 in Phase 2.

# 7.4 Thrombocytopenia

Another key observation made in the Phase 1 portion of this study is that none of our patients have experienced bone marrow suppression secondary to radiation and temozolomide outside of two instances of grade 1 thrombocytopenia in week 6 of radiation and chemotherapy.

In Phase 1, marked bone marrow protection has been observed as shown in Figure 3 below. In patients receiving temozolomide the standard of care is to stop therapy for patients developing a platelet count below 100,000. None of the fifteen evaluable subjects receiving BMX-001 + temozolomide developed platelet counts below 100,000. We compared this to patients that were not on protocol but had a diagnosis of glioblastoma (GBM) and were receiving radiation and TMZ and were being treated at the Duke Cancer Institute. In this control cohort, 9 out of 20 patients who

received concurrent TMZ and radiation therapy developed thrombocytopenia with platelet counts below 100,000. While these groups cannot be directly compared, the observation that subjects that received BMX-001 along with concurrent chemoradiation did not develop platelet counts below 100,000/mm^3 is compelling.

**Figure 3**. Platelet counts in high-grade glioma patients receiving temozolomide with and without BMX-001. Each line represents a separate patient. N=20 for patients receiving chemoradiation alone (left panel). N=15 for patients receiving BMX-001 + chemoradiation (right panel).

The data supports the conclusion that BMX-001 may be beneficial in preventing chemotherapyinduced bone marrow suppression at administered doses between 7 mg and 42 mg/subject load followed by one-half the loading dose administered biweekly.

Of note, there are now current studies underway with BMX-001 in radiation protection for mucositis and xerostomia in irradiated head and neck cancer patients, as well as a therapeutic for patients with

multiple brain metastases. With the information from these studies, we are confident in our toxicity pattern for BMX-001 in cancer patients and in the doses chosen for Phase 2 evaluation.

